Uppsala Spinal Stenosis Study (UppSten)

Decompression vs Non-surgical treatment for the lumbar spinal stenosis. An RCT with clinical, radiological, neurophysiological, histologic and biochemical follow-up

Background

Lumbar spinal stenosis (LSS) is characterized by low back and leg pain, walking disturbances and sometimes instability, impaired balance and numbness of the lower limbs. This condition is caused by degenerative changes in the lumbar spine including bulging discs, osteophytes from the arthritic facet joints and thickened ligamentum flavum which together cause narrowing of the spinal canal and thus affect the lumbar nerve roots. LSS affects mainly older populations and is unusual under 50 years old. This diagnosis is attracting more and more interest due to the aging population with increasing demands for physical activity. LSS is the most common indication for spinal surgery. The surgical treatment involves relieving the pressure from the nerve structures in the stenotic segments through a posterior approach. The hypertrophic ligaments and parts of the facet joints are removed (i.e., decompression). Adding fusion to the decompression for stabilization of the decompressed segment has not been shown to provide superior results than decompression alone [Försth] [Sigmundsson]. In several studies, surgery has been shown to have better results than the conservative treatment [Weinstein] [Malmivaara]. However, methodological difficulties and a large proportion of cross-over in these studies indicate that there is still uncertainty about whether surgery is generally a better option.

After decompression, only 60-70% of patients reported to be satisfied with the result and a minor proportion of them experienced even no improvement at all [Strömqvist]. Conservative treatment has shown in some studies to have good results for some patient groups [Delitto] and other studies have shown that the benefit of the surgical treatment decreases over time [Slätis] and that physical exercise may reduce the need for surgery [Nord]. Moreover, surgery itself has a positive placebo effect that can improve symptoms in some diseases [Harris].

It has been speculated whether the compression of the nerve roots causes in some patients permanent nerve damage with muscle denervation, while in other cases a reinnervation and recovery of the function may occur. Results from neurography and EMG studies have been shown these modalities to have a possible predictive value for the natural process of LSS [Adamova]. If a neurophysiological examination could be able to predict which patients are able to benefit from surgery, many patients could avoid surgery and the risks involved in it.

The degeneration of the lumbar spine is progressively impairing the spinal sagittal balance. The need to make extensive correction and fusion in addition to the decompression in order to restore the sagittal balance is debated among spinal surgeons. The experience gained from previous RCTs is that the patients' back pain is reduced by decompression only [Försth]. Many patients also report that their posture improved after decompression alone.

Previous trials in the connective tissue and blood samples have shown that proinflammatory factors and nociceptors (molecules that induce pain) are upregulated in patients with patellar tendinosis which is an inflammatory condition [Lian] [Schizas] [Schizas]. Changes in the connective tissue that cause LSS are mainly inflammatory (arthritic facet joints and ligamentum flavum) and a possible theory around LSS pathophysiology may be that the nerves are biologically affected by proinflammatory factors and nociceptors. Identification of some of these factors could lead to better explanation of the pathomechanism behind the nerve compression in LSS and to the development of future pharmacological treatments to be used in conjunction with surgery.

Aims

The aim of this study is primarily to evaluate whether surgery with decompression leads to superior results than the non-surgical treatment with structured physical therapy. For this evaluation, the Oswestry Disability Index (ODI) will be used.

The main secondary aim is to investigate by means of Neurography and EMG, whether the degree of neurological affection caused by nerve compression affects the outcome of surgery for LSS.

The questions at issue are:

1. Does decompression provide a better clinical outcome than the non-surgical treatment?
2. Is there any correlation between the grade of the clinical symptoms and the degree of neurological affection measured by ENG/EMG?
3. Is there any connection between the neurological affection and the proinflammatory markers/nociceptors in the blood as well as in histological findings from ligamentum flavum? Are these correlated with the grade of the clinical symptoms?
4. Does decompression provide superior neurological recovery, measured by ENG/EMG, in comparison to the non-surgical treatment?
5. Can decompression improve the spinal sagittal balance?

Inclusion criteria

1. Age 50-85 years.
2. Clinical symptoms of lumbar spinal stenosis (pseudoclaudication) that indicate and motivate surgery. NRS in lower limbs ≥ 3 .
3. MRI with finding of LSS at 1-3 lumbar levels. Dural sac area $\leq 75 \text{ mm}^2$ or degree of stenosis C or D according to Schizas classification.
4. The surgical treatment to be provided is decompression alone.
5. The patient has given oral and written informed consent to the participation in the study.

Exclusion criteria

1. Degenerative deformity with Cobb angle $> 20^\circ$.
2. Spondylolysis.
3. Symptomatic osteoarthritis of the lower limbs that affects and limits their function.
4. Arterial insufficiency (claudication intermittent).
5. Past lumbar surgery other than disc herniation.
6. Conditions that affect the spine such as ankylosing spondylitis, Diffuse Idiopathic Skeletal Hyperostosis (DISH), spondylodiscitis/infections, malignancy, neurological diseases.
7. Heart and lung diseases that present a significant risk for surgery or make it impossible for the patient to take part in physical training program (ASA >3).
8. Polyneuropathies.
9. Psychological factors that make the patient incapable of inclusion in the study (eg drug addiction, dementia)

Outcomes

Primary outcome: Oswestry Disability Index (ODI)

Secondary outcome:

Neurophysiology: Primary outcome measure: 1) Motor amplitude (neurography) and 2) Degree of Denervation Activity (EMG). Secondary outcomes: Sensory amplitude, F response latency and H-reflex (neurography), number of motor units (MUNIX) and degree of reinnervation (EMG).

From the Swedish Spine Registry (Swespine): EQ-5D, Back pain (NRS), Leg pain (NRS), Subjective walking ability, Global Assessment (GA), Satisfaction

Objective walking ability (6-Minute Walk Test-6MWT)

Radiological: Lumbar Lordosis (LL) and Sagittal Vertebral Axis (SVA)

Follow-up

6 months, 1, 2 and 5 years

The results at 2 years will be the most important goal of the study, on which the main clinical results will be built. The neurophysiological results can be analyzed and presented after the 6-month follow up.

Power calculation

Totally 150 patients will be included, 75 in each treatment group. The study size has been calculated with power 80% and $\alpha = 0.05$ as well as an ability to detect 12 units (SD19) of difference in the ODI, giving 40 follow-up patients in each group. Experience from previous registry-based RCTs within Swespine, regarding loss to follow-up and cross-over (ie patients admitted to non-surgical treatment who wish to switch to surgical intervention), is taken into account. According to this, the loss is considered to be low (<5% after 2 years) [Försth]. In previous studies, this proportion was comprised of 9 to 40% of the conservatively treated patients [Weinstein] [Malmivaara]. Loss to follow-up and cross-over are estimated to be up to 50%, which leads to 75 patients needed in each group.

Each year, 100-130 patients who meet the inclusion criteria are operated at the Department of Orthopaedics (Uppsala University Hospital and + Enköping Hospital). We estimate that 150 patients will be recruited to the study within a period of 24 months.

Flow-chart

Recruitment	The patient is recruited during an outpatient visit to a surgeon. Oral and written information about the study is given.
ICF	The patient gives oral and written consent. The consent is documented in the patient journal and the written consent is filed in the study document binder.
Baseline data	- PROMs via Swespine Study - 6MWT

	
 - Scoliosis standing digital X-rays (AP and lateral views) - ENG/EMG - Blood samples for analysis of inflammatory markers (OLINK)
Randomization	Simple block randomization to the two treatment arms.
Treatment arms	
A. Decompression. Central decompression of the stenotic segments with undercutting of the lateral recesses, free mobilization, and routine follow-up postoperatively by physiotherapist.
 
B. Non-surgical treatment. Exercise on exercise bike according to the "Östersund model" [Nord] 30 min, 3 times/week for 4 months.

Follow-up 6 months	
 - PROMs via Swespine Study - 6MWT - Scoliosis standing digital X-rays (AP and lateral views) - ENG/EMG - Blood samples for analysis of inflammatory markers (OLINK)
Cross-over	Feasibility for cross-over from group B till A after 6-month follow-up.
Follow-up 1,2 years	
 - PROMs via Swespine Study - 6MWT
Follow -up 5 years	
 - PROMs via Swespine Study

In the treatment group A, in conjunction with the surgical procedure, ligamentum flavum will be collected (which is routinely removed during the decompression surgery) and will be examined with histological methods regarding proinflammatory markers and nociceptors. An 1x1 cm tissue piece will be dissected and saved. The ligament samples will be examined by immunohistochemistry and with proteomics analysis. Proteomics analysis will be performed in collaboration with Olink Uppsala (www.olink.com) where 92 inflammation-related factors will be investigated. Sample management will be in accordance with the Ethics Examination Act of Human Research (2003: 460) and according to the rules of Uppsala Biobank.

References

Försth P, Michaëlsson K, Sandén B.

Does fusion improve the outcome after decompressive surgery for lumbar spinal stenosis?: A two-year follow-up study involving 5390 patients. *Bone Joint J.* 2013 Jul;95-B(7):960-5. doi: 10.1302/0301-620X.95B7.30776.

Försth P, Ólafsson G, Carlsson T, Frost A, Borgström F, Fritzell P, Öhagen P, Michaëlsson K, Sandén B.

A Randomized, Controlled Trial of Fusion Surgery for Lumbar Spinal Stenosis. *N Engl J Med.* 2016 Apr 14;374(15):1413-23. doi: 10.1056/NEJMoa1513721.

Sigmundsson FG, Jönsson B, Strömqvist B.

Outcome of decompression with and without fusion in spinal stenosis with degenerative

spondylolisthesis in relation to preoperative pain pattern: a register study of 1,624 patients. *Spine J.* 2015 Apr 1;15(4):638-46. doi: 10.1016/j.spinee.2014.11.020.

Malmivaara A, Slätis P, Heliövaara M, Sainio P, Kinnunen H; Finnish Lumbar Spinal Research Group.
Surgical or nonoperative treatment for lumbar spinal stenosis? A randomized controlled trial. *Spine (Phila Pa 1976).* 2007 Jan 1;32(1):1-8.

Weinstein JN, Tosteson TD, Lurie JD, Tosteson AN; SPORT Investigators.
Surgical versus nonsurgical therapy for lumbar spinal stenosis. *N Engl J Med.* 2008 Feb 21;358(8):794-810. doi: 10.1056/NEJMoa0707136.

Strömqvist B, Fritzell P, Hägg O, Jönsson B, Sandén B; Swedish Society of Spinal Surgeons.
Swespine: the Swedish spine register : the 2012 report. *Eur Spine J.* 2013 Apr;22(4):953-74. doi: 10.1007/s00586-013-2758-9.

Delitto A, Piva SR, Moore CG, Fritz JM, Welch WC.

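### Does the main secondary aim fail the protocol's own reason for measuring neurophysiology, because it does not ask who gains from surgery over exercise?

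*Protocol*

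**What the plan says.** The Background gives the practical reason for the neurophysiological work: "If a neurophysiological examination could be able to predict which patients are able to benefit from surgery, many patients could avoid surgery". Just before this, it contrasts permanent nerve damage in some patients with recovery of function in others. Earlier it reports that after decompression "a minor proportion of them experienced even no improvement at all", and it says of the literature in general: "Conservative treatment has shown in some studies to have good results for some patient groups".

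Under Aims, the main secondary aim is to find out "whether the degree of neurological affection caused by nerve compression affects the outcome of surgery for LSS". It names no comparator, outcome measure or time point. Two of the five numbered questions that follow concern neurophysiology and the clinical course: question 2, "Is there any correlation between the grade of the clinical symptoms and the degree of neurological affection measured by ENG/EMG", and question 4, "Does decompression provide superior neurological recovery, measured by ENG/EMG, in comparison to the non-surgical treatment". Question 1 is the overall treatment comparison, question 3 concerns inflammatory and histological markers, and question 5 concerns sagittal balance.

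The Flow-chart places ENG/EMG and patient-reported outcomes at baseline, before randomisation, and again at 6 months, in both arms. Cross-over from exercise to surgery opens only after the 6-month visit. Under Follow-up, the main clinical results rest on 2 years, while "The neurophysiological results can be analyzed and presented after the 6-month follow up".

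**The concern.** Deciding who can avoid surgery calls for knowing who does better with surgery than with exercise. That is a question of effect modification: does the difference in ODI between arms vary with the baseline marker? A marker that goes with poor outcome under either treatment would also correlate with outcome among operated patients, yet would say nothing about whether those patients should be operated on.

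The aim, read as a question about operated patients, does not draw this distinction, and no numbered question does so either. If only the association within the surgical arm were reported, a reader might take a general prognostic marker for a guide to treatment choice. The trial also has what the other question needs: the marker is measured before randomisation in both arms, and there is a 6-month outcome before planned cross-over. The omission therefore looks like a missed opportunity in the wording of the aims.

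**Working it through.** **1. The texts side by side.** For the aim to contradict the motivation, the motivation would have to require a comparison with exercise and the aim would have to exclude one. Neither is so.

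- The motivating sentence speaks of patients able to benefit from surgery. Its context is nerve damage that may or may not recover, and the Background has already noted patients with no improvement after decompression. Identifying patients unlikely to improve after surgery is a natural reading, and the aim addresses it directly.
- The remark about conservative treatment and some patient groups is a general statement about the literature. It is not tied to neurophysiology.
- The aim names no comparator, but it does not restrict the population either. No sentence in the protocol limits the analysis to the surgical arm.
- Questions 2 and 4 ask other things (a correlation with symptoms, and ENG/EMG as an outcome). They do not contradict the aim.

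**2. The plan's own figure.** Inputs from Power calculation: difference 12, SD 19, power 80%, α = 0.05 (taken as two-sided).

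n per group = 2 × (1.960 + 0.842)² × (19/12)² = 2 × 7.849 × 2.507 = 39.4, rounded up to 40. This reproduces the stated 40, so the point involves no numerical error.

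**3. Can a prognostic result stand in for an interaction?** Assume a purely prognostic marker with equal slopes in both arms and 71 per arm (75 × 0.95, using the protocol's 5% loss). In 20,000 simulated trials per setting, at assumed correlations of 0.2, 0.3 and 0.4, the association within the surgical arm is significant in 38%, 74% and 94% of trials, and the interaction in about 5%. The first set are correct rejections, because the marker really is prognostic. The 5% follows from the assumption of no interaction. So the two questions differ, but nothing here shows that the prognostic question is answered wrongly.

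**4. What the extra question could deliver.** Take 6-month ODI, with SD 19 assumed to hold at that visit, and m patients per arm.

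- Continuous marker, per marker SD: SE = 2 × 19/√(2m). For m = 71, 38/√142 = 3.19, and the detectable interaction at 80% power is 2.80 × 3.19 = 8.9 points. For m = 75, SE = 3.10 and the detectable interaction is 8.7 points.
- Yes/no marker with prevalence p: SE = 19 × √(2/(mp) + 2/(m(1−p))).

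| m per arm | p (assumed) | SE | Detectable at 80% power | Power for 12 points |
|---|---|---|---|---|
| 75 | 0.5 | 6.21 | 17.4 | 49% |
| 75 | 0.3 | 6.77 | 19.0 | 43% |
| 71 | 0.5 | 6.38 | 17.9 | 47% |
| 71 | 0.3 | 6.96 | 19.5 | 41% |

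As an example of the last column, Φ(12/6.38 − 1.96) = Φ(−0.08) = 0.47. Simulation gives nearly the same: 18 to 20 points detectable, and 40 to 48% power for 12 points.

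At 2 years with 71 per arm, if cross-over is random and carries the full surgical effect (assumptions), a continuous marker needs about 10 points per SD at 9% cross-over and about 17 at 40%. The 9% and 40% are the range quoted in Power calculation.

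**5. Meaning of these figures.** For a yes/no marker, the smallest interaction likely to be detected exceeds the 12 points that the trial is sized to find for the whole treatment effect. Leaving such an analysis off the list of numbered questions is a defensible choice.

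**The case for a change.** The strongest opposing argument is that the choice of question belongs to the protocol, whatever is left to the analysis plan. The protocol lists its questions, and the one that most directly serves the hope of sparing patients surgery is not among them. Adding it would cost one question and one regression per marker on data already collected, reported as an exploratory estimate with a confidence interval.

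Part of this stands. A within-surgery association alone would not justify withholding surgery, and a report that drew that conclusion would overreach. It is also true that no numbered question restates the main secondary aim.

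The argument does not establish a defect, though. The harm depends on only the within-surgery association being reported, and the protocol does not say that it will be. Population, model and time point are commonly left to a statistical analysis plan, and the data needed for an interaction are collected in both arms, so the protocol closes no door.

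The cost is not quite trivial either. Outcomes names motor amplitude and denervation activity as the main neurophysiological measures but no nerve, muscle or side, so the number of estimates is unknown. An interaction model on 6-month ODI also contains the comparison between arms. If it were released with the early neurophysiological results, that contrast would become known before the 2-year follow-up was complete.

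**Conclusion.** The concern does not hold. The main secondary aim poses a sound prognostic question that fits the Background, and following it as written gives a valid answer to that question. The protocol neither contradicts itself here nor rules out a comparison with the exercise arm.

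What is left is a preference for an additional exploratory analysis of limited precision: about 9 ODI points per marker SD, or about 17 to 20 points for a yes/no marker, for 80% power at 6 months. These figures assume SD 19 at 6 months, 71 to 75 patients per arm, and a marker prevalence of 30 to 50%, which the protocol does not give. The conclusion does not depend on them, because it rests on the wording of the Background and Aims and on the absence of any restriction to operated patients.

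### The sample size treats cross-over as dropout, so the 80% power for the 2-year ODI result is not assured over the 9–40% cross-over range the protocol cites

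*Protocol*

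**What the plan says.** The Follow-up section places the main clinical result at 2 years: "The results at 2 years will be the most important goal of the study, on which the main clinical results will be built". The flow-chart's cross-over row reads "Feasibility for cross-over from group B till A after 6-month follow-up", so operated patients from group B can contribute to the 2-year ODI up to 18 months after cross-over opens. Question 1 under Aims asks: "Does decompression provide a better clinical outcome than the non-surgical treatment".

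The power calculation uses 80% power, alpha 0.05 and a detectable difference of 12 ODI units with SD 19, "giving 40 follow-up patients in each group". It puts loss below 5% at 2 years. On cross-over it says: "In previous studies, this proportion was comprised of 9 to 40% of the conservatively treated patients". It then combines the two: "Loss to follow-up and cross-over are estimated to be up to 50%, which leads to 75 patients needed in each group". The 12 units are not changed at that step.

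**The concern.** Dividing a required sample size by the share of patients retained is the right adjustment for missing data, because missing patients take information away but leave the target difference alone. Cross-over works differently.

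- **Patients kept as randomised.** Operated patients remain in arm B, and the expected difference moves towards zero. The number needed then grows with the square of the dilution.
- **Patients who cross over set aside.** The 12 units survive only if those patients would have done as well without surgery as the patients who stay on exercise.

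The pooled allowance therefore does not secure 80% power under either approach without a further assumption, and the protocol states none.

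Two things are at stake. First, the stated power may not hold at the upper end of the cross-over range the protocol itself cites. Second, a small 2-year difference would be hard to read: it could mean little benefit, dilution by cross-over, or the waning the Background reports ("other studies have shown that the benefit of the surgical treatment decreases over time"). The Background also gives heavy cross-over in previous trials as a reason why the question is still open.

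**Working it through.** **Inputs from the protocol.** Difference 12, SD 19, alpha 0.05 (two-sided assumed, which reproduces the stated figure), power 80%, 75 randomised per group, loss below 5%, cited cross-over 9–40%, joint allowance up to 50%.

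**Step 1: the plan's own figure.** n per group = 2 × (1.960 + 0.842)² × (19/12)² = 39.4, rounded up to 40. This agrees with the protocol. Power at 40 per group is 80.6% by the normal approximation and 79.7% by the noncentral t.

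**Step 2: the inflation.** 1 − 40/75 = 46.7% set aside. A full 50% would give 40/0.5 = 80. Since the text says up to 50%, 75 is compatible with it. Either way, this is a dropout-type inflation.

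**Step 3: analysed as randomised.** Let c be the share of arm B that crosses over and b the share of the surgical benefit those patients have at 2 years.

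- Expected difference = 12 × (1 − c·b), assuming 12 is the effect before cross-over.
- Evaluable per arm = 75 × 0.95 = 71.25, taken as 71.
- SD in arm B is either held at 19 or allowed to widen because the arm mixes operated and unoperated patients: √(19² + c(1 − c)(12b)²). At c = 0.40 and b = 1 this is √(361 + 0.24 × 144) = 19.9.
- Power comes from the noncentral t, two-sided 0.05.

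| Cross-over c | Benefit b | Difference | Power, SD 19 | Power, mixture SD |
|---|---|---|---|---|
| 0% | – | 12.0 | 96% | 96% |
| 9% | full | 10.9 | 92.5% | 92% |
| 25% | full | 9.0 | 80.0% | 79% |
| 40% | full | 7.2 | 61% | 59% |
| 40% | three-quarters | 8.4 | 74% | 73% |
| 40% | half | 9.6 | 85% | 84% |

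**Step 4: where power falls to 80%.** With SD 19, the limit is c·b ≈ 0.25. With the mixture SD, the tolerated cross-over is about 24% at full benefit (23.7%), 32% at three-quarters and 49% at half. At 40% cross-over, power drops below 80% once b exceeds about 0.61 (mixture SD) to 0.63 (SD 19, 0.25/0.40).

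**Step 5: cross-overs set aside instead.** Let g be how many points worse those patients would have been than the stayers without surgery (assumed values). Contrast = 12 − c·g, with 71 against 71 × (1 − c) patients.

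- c = 25% (71 v 53): g = 0 gives 12.0 and 93%; g = 5 gives 10.75 and 87%; g = 10 gives 9.5 and 78%.
- c = 40% (71 v 43): g = 0 gives 12.0 and 90%; g = 5 gives 10.0 and 77%; g = 10 gives 8.0 and 58%.

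**Step 6: precision at 6 months.** The 95% CI half-width for the ODI contrast is t(140) × 19 × √(2/71) = 6.3 points.

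**The case against.** **The analysis may be defined elsewhere.** The analysis set and the handling of ODI after cross-over are commonly left to a statistical analysis plan, and none is at hand. This stands, and their absence is not the point here. The pooling of cross-over with loss, however, is fixed in the protocol's own power calculation.

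**The 12 units may already allow for cross-over.** The text presents 12 only as the difference the trial can detect; it does not call it the effect under full adherence. If 12 is the difference expected at 2 years with cross-over included, 71 per arm gives 96% power. An undiluted effect of 15 would give 15 × 0.6 = 9.0 points at 40% full-benefit cross-over, and 80% power with SD 19. This also stands. It makes the power figures conditional and is a reason to say what the 12 units mean.

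**A reader might infer that 80% power fails over much of the range whatever is assumed.** The figures do not support that. With half benefit, power is still 84–85% at 40% cross-over, and excluding cross-overs of equal prognosis leaves 90%.

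**A reader might infer a planned cross-over ceiling of 45%.** The protocol states no such rate. It is only the joint 50% allowance less the 5% loss; the cited cross-over range ends at 40%.

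**A reader might infer that the 6-month visit is reserved for neurophysiology, leaving the 6-month ODI unused.** The sentence is permissive: "The neurophysiological results can be analyzed and presented after the 6-month follow up". ODI is the primary outcome, patient-reported outcomes are scheduled at 6 months, question 1 has no time point, and calling the 2-year results the main ones does not exclude others.

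**Conclusion.** The point holds in a limited form. The base size of 40 is right. The step to 75 handles cross-over as dropout, which matches neither an as-randomised analysis nor, without an equal-prognosis assumption, an analysis that sets those patients aside.

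Taking 12 units as the undiluted effect, with SD 19, 71 evaluable per arm and two-sided 0.05, the stated 80% is not assured across the cited 9–40%. It holds comfortably at the low end and to about 24% cross-over even with full benefit. It fails at 40% if those who cross over gain more than roughly 60% of the benefit, reaching 59–61% in the full-benefit case. The share of benefit gained is not given in the protocol and had to be assumed.

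The as-randomised 2-year contrast compares early surgery with exercise first and later surgery possible. That is a legitimate comparison, but the protocol should say that this is how its main result bears on question 1. Severity is low: the design can stand, and the stated power needs its conditions.

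**What to change.** Keep the 2-year time point, the sample size and the cross-over provision. In the power calculation:

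1. Separate cross-over from loss to follow-up, and inflate only for loss.
2. Say whether 12 units is the difference before cross-over or already allows for it.
3. State that the 2-year result, analysed as randomised, compares early surgery with exercise first and later surgery possible.
4. If 12 units is the difference before cross-over, restate the power as conditional: with 75 per group and 5% loss, 80% holds up to about 24% cross-over with full benefit, about 32% with three-quarters and about 49% with half (mixture variance in arm B).

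This costs a few sentences.

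An optional improvement, not the correction of an error, is to pre-specify the 6-month ODI contrast as a supportive secondary estimate with its 95% CI (half-width about 6.3 points). The data are already scheduled, after the 4-month exercise programme and before planned cross-over. Its limits should be stated: it is short-term, patient-reported and open to the placebo effect of surgery that the Background mentions. Nor can it separate dilution from waning, since 25% full-benefit cross-over and a 25% loss of effect without cross-over both give 12 × 0.75 = 9.0 points at 2 years. Its place in any testing order can be left to the statistical analysis plan.

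### Does presenting the 6-month neurophysiological results before the 2-year ODI is complete put the primary comparison at risk?

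*Protocol*

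**What the plan says.** The Follow-up section sets visits at "6 months, 1, 2 and 5 years" and ranks them: "The results at 2 years will be the most important goal of the study, on which the main clinical results will be built". It then allows an earlier report for one domain: "The neurophysiological results can be analyzed and presented after the 6-month follow up".

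Four other places bear on this:

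- **Aims, question 4** makes part of the neurophysiology a randomised comparison: "Does decompression provide superior neurological recovery, measured by ENG/EMG, in comparison to the non-surgical treatment".
- **Flow-chart** schedules ENG/EMG at baseline and at 6 months. The 1- and 2-year visits have patient-reported measures and the 6-minute walk test; the 5-year visit has patient-reported measures only.
- **Flow-chart, Cross-over row**: "Feasibility for cross-over from group B till A after 6-month follow-up". No closing date is given.
- **Power calculation**: "Totally 150 patients will be included, 75 in each treatment group", and "We estimate that 150 patients will be recruited to the study within a period of 24 months".

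The ODI is the primary outcome and is patient-reported. The arms are decompression surgery and cycling exercise, and no blinding is described.

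**The concern.** Because question 4 compares the arms and 6 months is the only ENG/EMG visit after baseline, the permission to present covers a by-arm result. The Protocol does not limit it to pooled data or say who may see it. By-arm results could thus be public while many patients have yet to give the 2-year ODI.

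Two routes to bias suggest themselves. Patients who learn that one arm did better neurologically might answer the ODI differently. Group B patients, or their surgeons, might be moved towards cross-over, which would dilute the comparison as randomised. The Background section makes both worth a thought: it credits surgery with a placebo effect and names heavy cross-over as a weakness of earlier trials. If either route were real, the primary comparison would be affected.

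**Working it through.** **1. The plan's own figure.** For a difference of 12 with SD 19, two-sided alpha 0.05 and 80% power, n per group = 2 × (1.960 + 0.842)² × 19² / 12² = 39.4, rounded up to 40. This matches the Power calculation section. Nothing in the reporting sentence enters this formula.

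**2. Timing.** Let recruitment last R months. The last 6-month visit falls at R + 6 and the last 2-year visit at R + 24, so the gap is 18 months whatever R is. With R = 24 these are months 30 and 48.

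**3. How many still owe the 2-year ODI.** Assume uniform recruitment and release L months after the last 6-month visit. Both are assumptions; the Protocol gives neither a recruitment pattern nor a release date. The share with less than 24 months of follow-up at month R + 6 + L is (18 − L)/R.

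| Lag L (months) | R = 24 | Of 150 | Of 75 in group B | R = 36 |
|---|---|---|---|---|
| 0 | 75% | about 112 | about 56 | 50% |
| 6 | 50% | 75 | about 37 | 33% |
| 12 | 25% | about 38 | about 19 | 17% |
| 18 | 0% | 0 | 0 | 0% |

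R = 24 needs 75 patients a year, which is 58–75% of the 100–130 eligible patients stated. R = 36 is an assumed slower case of 50 a year (38–50%). The top row leaves no time for cleaning, analysis or writing.

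**4. Where the remaining group B patients stand.** Among those still owing the ODI, time since the 6-month visit runs evenly from L to 18 months, with mean (L + 18)/2: 9, 12 or 15 months at lags of 0, 6 or 12. Cross-over has been open to them for that long on average, so many of these decisions would already have been made. The group B counts also include patients who have already crossed over.

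**5. What the sentence releases.** It names neurophysiological results only. ENG/EMG is not scheduled after 6 months, so this is the final analysis of that domain at a time fixed in advance. No test of the 2-year ODI is brought forward and the type I error of the primary comparison is unchanged. Question 2 and the main secondary aim, which relates nerve involvement to the outcome of surgery, are not comparisons between arms.

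**6. Does the text conflict with itself?** The Follow-up section ties the main clinical results to 2 years and lets neurophysiology report after 6 months. These are two outcome domains with two reporting times, and both statements can be followed together.

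**The case for a change.** The strongest case for the concern is that the permission is explicit, so an unseen SAP restricting release would have to be reconciled with it. The 18-month gap is certain, and the primary outcome is patient-reported in a trial with no blinding described. The Protocol suggests that neurophysiology may predict who benefits from surgery, which makes a by-arm result relevant to a group B patient weighing cross-over. If release were allowed before the last patient's 6-month visit, exposure would exceed the table. All of this stands.

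The step from exposure to harm does not. Patients would know which treatment they had and how they feel. Nothing in the Protocol indicates that group-level motor amplitude or denervation findings would reach them or change their answers. Cross-over opens at 6 months with or without a report.

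A power illustration can be built. Take 71 patients per group (75 less 5% loss) and dilute the difference to 12 × (1 − c) for cross-over share c. Power is then 93%, 85% and 62% at c = 9%, 20% and 40%. If release led a further 10% of the 75% of group B still waiting to cross over, c would rise by 0.10 × 0.75 = 7.5 points and power would fall to 88%, 78% and 51%. The arithmetic is right, but the extra 10% comes from nowhere in the documents, so the drop restates the assumption. The range of 9–40% that the Protocol cites from earlier trials moves power much further with no early report involved.

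Withholding also has a cost. By-arm reporting of the main secondary domain would be delayed by up to 18 months. Keeping a completed analysis from treating staff would need an analyst separate from them, and the Protocol names none.

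**Conclusion.** The concern does not hold. The Protocol sets, in advance, when a secondary outcome that is complete at 6 months may be reported. This is no interim look at the 2-year ODI, no figure in the Protocol is wrong because of it, and the passages agree with each other.

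The size that can be stated is exposure: between 75% and 0% of patients still owing the 2-year ODI with 24-month recruitment, and between 50% and 0% with 36 months, for lags of 0 to 18 months. This rests on assumed uniform recruitment and assumed lags. No effect on ODI answers, cross-over or power can be derived from the documents. Some statisticians would hold by-arm results until the last 2-year ODI; others would not delay a finished analysis by up to 18 months for an influence that has not been shown. That is a judgement about release timing, and the Protocol's choice is defensible.
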